## **6.7 BASELINE, TIME WINDOWS AND CALCULATED VISITS**

With regard to effectiveness and safety endpoints, the term "baseline" refers to the last observed measurement prior to administration of TRADIANCE®. Observation on the same day as administration of TRADIANCE® is "baseline".

Effectiveness analyses will be performed based on calculated visits as shown in [Table 6.7: 1](#). If two or more data points of a patient fall into the same interval, the closest value to the planned day will be selected. If there are two observations which have the same difference in days to the planned day or if there are two observations on the same day, the first value will be used.

Table 6.7:1 Baseline, time windows and calculated visits

Week label	Planned days	Time window (actual days on treatment)	
		Start	End
Baseline	0	NA	1
Week12	84	2	133
Week26	182	134	231
Week40	280	232	322
Week52/EOT	364	323	End of study

## **7. PLANNED ANALYSIS**

For End-Of-Treatment (EOT) tables, the set of summary statistics is: N / Mean / SD / Min / Q1 / Median / Q3 / Max. For tables that are provided for endpoints with some extreme data, median, quartiles and percentiles should be preferred to mean, standard deviation, minimum and maximum.

Tabulations of frequencies for categorical data will include all possible categories and will display the number of observations in a category as well as the percentage (%) relative to the respective treatment group (unless otherwise specified, all patients in the respective patient set whether they have non-missing values or not). Percentages will be rounded to 2 decimal places. The category missing will be displayed only if there are actually missing values. Caution: Frequencies for combination drugs of antidiabetic medication must be tabulated by each active pharmaceutical ingredient.

In addition, individual values on demographics, safety and effectiveness will be presented in subject data listings.

### **7.1 DEMOGRAPHIC AND OTHER BASELINE CHARACTERISTICS**

Only descriptive statistics are planned for this section of the report.

### **7.2 CONCOMITANT DISEASES AND MEDICATION**

Concomitant diseases will be coded by the latest version of Medical Dictionary for Regulatory Activities (MedDRA). Frequency of patients will be summarized by system organ class (SOC) and preferred term (PT).

Concomitant medication will be coded by latest version of “Nihon Iyakuhinshu” ([2](#)).

### **7.3 TREATMENT COMPLIANCE**

[figure not shown]
Compliance data is not collected in this study

### **7.4 PRIMARY ENDPOINT (S)**

The primary outcome of this study is the incidence of adverse drug reactions (ADRs). For the analysis of the primary endpoint, see [Section 7.8](#).

### **7.5 SECONDARY ENDPOINT (S)**

None

## **7.7 EXTENT OF EXPOSURE**

Only descriptive statistics are planned for this section of the report.

## **7.8 SAFETY ANALYSIS**

All safety analyses will be performed on the treated set.

### **7.8.1 Adverse events**

Unless otherwise specified, the analyses of adverse events will be descriptive in nature. All analyses of AEs will be based on the number of patients with AEs and NOT on the number of AEs.

For further details on summarization of AE data, please refer to the guideline “Analysis and Presentation of Adverse Event Data from Clinical Trials” ([3](#)).

AE analyses will be carried out after integrating AE data from CRF and AE data from perceive system. In addition, AEs coded as “no adverse event” will not be included in the AE analyses.

The analysis of adverse events will be based on the concept of treatment emergent adverse events. That means that all adverse events occurring between first drug intakes till 7 days after last drug intake during observation period will be analysed. For details on the treatment definition, see [Section 6.1](#).

An overall summary of adverse events will be presented.

The frequency of patients with AEs, severe AEs, drug related AEs, AEs leading to discontinuation, drug related AEs leading to discontinuation, outcome for serious AEs and outcome for serious drug related AEs are tabulated.

The frequency of patients with AEs, ADRs, SAEs and SADRs will be summarised by primary system organ class and preferred term. Patients with ‘priority survey items’ according to the drug’s Risk Management Plan will be summarised separately. The analysis of “priority survey items”, “Important identified risks”, “Important potential risks” will be conducted for AEs, ADRs.

It is created that table of patient with ADRs in each subgroup defined in [Section 6.4](#). Not only the frequency but also the odds ratios are displayed.

In addition summaries for the time to onset of first episode for the ADRs will be tabulated, by duration (<= 12 week, 12 to <=26 weeks, 26 to <=52 weeks, > 52), by primary system organ class and preferred term.

Adverse events leading to death and adverse events leading to discontinuation will be also summarised by treatment, primary system organ class and preferred term.

An ADR is defined as an AE for which either the investigator or the sponsor (or both) assess the causal relationship to TRADIANCE® as “Yes”. A SAE is defined as an AE for which either the investigator or the sponsor (or both) assess the seriousness either as “Serious”.

The system organ classes will be sorted according to the standard sort order specified by EMA, preferred terms will be sorted by frequency (within system organ class).

The following AEs are detected on the basis of the Standardised MedDRA queries (SMQs) or Boehringer Ingelheim customised MedDRA query (BICMQ) (details are described in ADS plan).

Safety will be assessed by treatment exposure time adjusted incidence rate (n in 100 patient years) of ADRs.

Important identified risk, Important potential risk and significant ADRs.

The following AEs are summarised on the basis of the Standardised MedDRA queries (SMQs) or Boehringer Ingelheim customised MedDRA query (BICMQ) by primary SOC and PT.

\*: ADRs are also summarised.

Important identified risks

- Urinary tract infection \*
- Genital infection \*
- Volume depletion \*
- Hypoglycaemia \*
- Pancreatitis \*
- Ketone body increase/Ketoacidosis \*
- Polyuria/Pollakiuria \*
- Intestinal obstruction \*
- Hepatic function disorders \*

Important potential risks

- Renal disorder \*
- Bone fracture \*
- Skin lesion \*
- Bullous pemphigoid \*
- Interstitial pneumonitis \*
- Infection \*
- Malignant tumour \*
- Cardiac failure \*
- Influence of weight decreased on safety \*
- Lower limb amputation \*

Risk ratios with 95% confidence intervals will be shown for subgroup analysis. In case that there will be the significant difference each factor, the frequency of patients with ADRs and with serious AEs will be summarized by primary SOC and PT. Due to the high number of exploratory subgroup analyses, it is recognised that the likelihood of chance findings is high and therefore subgroup results should be interpreted with caution.

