4. ABSTRACT

Name of company: Boehringer Ingelheim			
Name of finished medicinal product: TRADIANCE® Combination Tablets AP, BP			
Name of active ingredient: Empagliflozin, Linagliptin			
Protocol date: 8 December 2017	Study number: 1275.0026	Version/Revision: Version 2.0	Version/Revision date: 20 November 2018
Title of study:	Post Marketing Surveillance in Japan on Long Term Drug Use of TRADIANCE® Combination Tablets AP and BP in Patients with type 2 Diabetes Mellitus		
Rationale and background:	
In Japan, post-approval execution of Post Marketing Surveillance is requested by the Japanese Pharmaceuticals and Medical Devices Act (J-PMD Act) in order to accumulate safety and efficacy data for re-examination. Re-examination period is defined by J-PMD Act. Four years after approval of combination drugs, results of PMS need to be submitted as a part of re-examination dossier to the Japanese regulatory authority, the Ministry of Health, Labour and Welfare (MHLW).
 
Collected data from PMS will be included in the Japanese periodic safety reports and submitted to MHLW on designated dates until the end of re-examination period.
		
Research question and objectives:	Study objective is to investigate the safety of long-term daily use of TRADIANCE® Combination Tablets AP and BP in Japanese patients with type 2 Diabetes Mellitus under real-world use.		
Study design:	
Cohort study
 
Non-interventional, single arm study based on newly collected data
 
Patients will be observed for up to 52 weeks after start of the treatment with TRADIANCE® Combination Tablets AP or BP or until discontinuation of administration.
		
Population:	
Inclusion criteria
 
- Japanese patients with type 2 Diabetes mellitus who are prescribed with TRADIANCE® Combination Tablets AP or BP- Patients who have never been treated with TRADIANCE® Combination Tablets AP or BP before enrolment 
Exclusion criteria
 
None
		

Name of company: Boehringer Ingelheim			
Name of finished medicinal product: TRADIANCE® Combination Tablets AP, BP			
Name of active ingredient: Empagliflozin, Linagliptin			
Protocol date: 8 December 2017	Study number: 1275.0026	Version/Revision: Version 2.0	Version/Revision date: 20 November 2018
Variables:	
Outcomes: Primary outcome: Incidences of adverse drug reactions (ADRs)
 
Secondary outcomes: None
 		

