Arguments that may suggest that there is **no reasonable possibility of a causal relationship** could be:

- No plausible time to onset of the event relative to the time of drug exposure is evident (e.g. pre-treatment cases, diagnosis of cancer or chronic disease within days/weeks of drug administration; an allergic reaction weeks after discontinuation of the drug concerned)
- Continuation of the event despite the withdrawal of the medication, taking into account the pharmacological properties of the compound (e.g. after 5 half-lives). Of note, this criterion may not be applicable to events whose time course is prolonged despite removing the original trigger.
- Additional arguments amongst those stated before, like alternative explanation (e.g. situations where other drugs or underlying diseases appear to provide a more likely explanation for the observed event than the drug concerned).
- Disappearance of the event even though the study drug treatment continues or remains unchanged.

Intensity of adverse event

The intensity of the AE should be judged based on the following:

Mild: Awareness of sign(s) or symptom(s) which is/are easily tolerated

Moderate: Enough discomfort to cause interference with usual activity

Severe: Incapacitating or causing inability to work or to perform usual activities

Pregnancy:

In rare cases, pregnancy might occur in a study. Once a subject has been enrolled into the study, after having taken TRADIANCE® Combination Tablets AP or BP, the investigator must report any drug exposure during pregnancy, which occurred in a female subject or in a partner to a male subject to the Sponsor by means of Part A of the Pregnancy Monitoring Form. The outcome of the pregnancy associated with the drug exposure during pregnancy must be followed up and reported by means of Part B of the Pregnancy Monitoring Form.

In the absence of a reportable AE, only the Pregnancy Monitoring Form must be completed, otherwise the Non-interventional Study AE form is to be completed and forwarded as well as soon as possible.

Priority survey items:

Fluid volume decreased events and Hypoglycaemia (important identified risks), safety of administration to patients with renal impairment or elderly patients (important missing information) stated in the Japan Risk Management Plan

Information required

For each reportable adverse event, the investigator should provide the information requested on the appropriate (e)CRF pages.

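### Subgroup ADR contrasts in SAP 7.8.1 are crude ratios of patient counts; if time on drug differs between subgroups they are biased, in either direction, and no time-adjusted contrast is stated

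*SAP*

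**What the plan says.** **Observation time.** The abstract of the Protocol has patients observed for at most 52 weeks "or until discontinuation of administration". SAP 7.8.1 counts events from first intake "till 7 days after last drug intake during observation period will be analysed". Time at risk therefore depends on how long each patient stays on the drug.

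**Counting unit.** SAP 7.8.1: "All analyses of AEs will be based on the number of patients with AEs and NOT on the number of AEs".

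**Subgroup measure.** SAP 7.8.1 gives two. For the table of patients with ADRs by subgroup: "Not only the frequency but also the odds ratios are displayed". Later in the section: "Risk ratios with 95% confidence intervals will be shown for subgroup analysis". Neither is said to account for time at risk. A significant difference on a factor leads to further tables of ADRs and serious AEs by system organ class and preferred term. The section does not say which measure or level decides this.

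**Exposure adjustment.** The same section says: "Safety will be assessed by treatment exposure time adjusted incidence rate (n in 100 patient years) of ADRs". It mentions neither subgroups nor a rate ratio.

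**Populations of interest.** The priority survey items in Protocol 11.2 include "safety of administration to patients with renal impairment or elderly patients (important missing information". SAP 7.8.1 points to SAP 6.4 for the subgroup definitions. That section is not in the public text, so the factors cannot be read there.

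**The concern.** A proportion of patients with an ADR treats someone who stopped at week 8 like someone observed for 52 weeks. If one subgroup stops earlier for reasons other than an ADR, it has less opportunity to show one, and its crude risk is lower for the same hazard. The ratio between subgroups then mixes a difference in ADR hazard with a difference in persistence.

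Two things depend on it. Age and renal function are where the Protocol says information is missing, so contrasts on those factors would be read with interest. The significance rule also means that a distorted ratio can suppress the detailed tables or set them off without cause. The SAP's own caution about subgroups concerns chance findings, not unequal follow-up.

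**Working it through.** The plan gives no figure for this comparison. The power statement in Protocol 9.5 concerns hypoglycaemia against a fixed 1.1% and does not bear on it; only the 1000 patients are used below.

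**Assumed inputs (none is in the documents).** ADR risk in the reference group 10% over 52 weeks of uninterrupted treatment; true rate ratio 1.5; constant hazards; stopping unrelated to ADR risk within a subgroup; 10% of the reference group stop within 52 weeks. The 7-day tail after last intake is ignored.

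**Formulas.** With time in years (52 weeks = 1), a one-year probability p corresponds to hazard −ln(1 − p). With ADR hazard λ and stopping hazard d, the crude risk is λ/(λ + d) × [1 − exp(−(λ + d))].

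**Reference group.** λ = −ln(0.90) = 0.1054 and d = 0.1054. Crude risk = 0.5 × [1 − exp(−0.2107)] = 0.0950.

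**Subgroup.** λ = 1.5 × 0.1054 = 0.1580.

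| Subgroup stopping | d | Crude risk | Crude risk ratio | Crude odds ratio |
|---|---|---|---|---|
| 10% | 0.1054 | 0.1389 | 1.46 | 1.54 |
| 20% | 0.2231 | 0.1314 | 1.38 | 1.44 |
| 30% | 0.3567 | 0.1235 | 1.30 | 1.34 |
| 40% | 0.5108 | 0.1152 | 1.21 | 1.24 |

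The person-time rate ratio is 1.50 in every row. The first row shows that a risk ratio sits slightly below a rate ratio even with equal stopping; the further fall is due to persistence. Odds ratios are attenuated in the same way.

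**Effect on the significance rule.** Take 400 patients in the subgroup and 600 in the reference group, with 30% against 10% stopping. Expected patients with an ADR are 400 × 0.1235 = 49.4 and 600 × 0.0950 = 57.0.

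- Crude risk ratio: SE(log) = √[(1 − 0.1235)/49.4 + (1 − 0.0950)/57.0] = 0.183, giving 1.30 (0.91 to 1.86).
- Rate ratio: SE(log) = √(1/49.4 + 1/57.0) = 0.194, giving 1.50 (1.02 to 2.20).

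One interval includes 1 and the other does not. With only 100 patients in the subgroup both include 1: 1.30 (0.74 to 2.28) and 1.50 (0.83 to 2.72). The choice of measure then changes the estimate but not the decision.

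**Direction.** Take no true difference, the same 10% risk, and all stops at week 12. Risk to week 12 is 1 − exp(−0.1054 × 12/52) = 0.0240.

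- 10% stopping: 0.9 × 0.10 + 0.1 × 0.0240 = 0.0924.
- 40% stopping: 0.6 × 0.10 + 0.4 × 0.0240 = 0.0696.

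If the subgroup stops more, the crude ratio is 0.0696/0.0924 = 0.75. If the reference group stops more, it is 0.0924/0.0696 = 1.33, a false excess.

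**The case against.** **No evidence of unequal follow-up.** The documents give no discontinuation rate, overall or by subgroup. With equal stopping almost nothing is lost (1.46 against 1.50). This stands: the size is conditional. The plan is nevertheless fixed before persistence is known, and the fix does no harm if it proves equal.

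**Stops caused by an ADR.** Such a patient is already a case, so the shortened exposure does not lower the crude proportion. This stands: only other stopping biases the ratio.

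**A rate ratio can mislead too.** If ADRs cluster early and stopping comes later, equal crude risks over mean follow-up of 0.6 against 0.9 year give a rate ratio of about 0.9/0.6 = 1.5 with no true difference. This stands against a constant-rate Poisson model. It does not apply to a hazard ratio for time to first ADR, or to a Poisson model with follow-up period terms.

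**Silence and context.** The exposure-adjusted rate is stated generally and could be produced by subgroup; SAP 6.4 and the guideline cited for AE presentation are not visible. Priority survey items are summarised separately, analyses are descriptive, Protocol 9.9 acknowledges loss to follow-up and disclaims comparisons, and the SAP calls the subgroup work exploratory. This limits the weight of the point. It does not remove it, because the SAP still attaches intervals and a significance rule to the ratios, and the visible text names only crude ones.

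**A stronger reading.** A reader might infer that elderly or renally impaired patients stop sooner and that a real excess among them will be hidden. The documents do not support that: they say nothing on who stops earlier, the bias can run the other way, and these factors cannot be confirmed for this table. The same applies to scenarios in which a true 1.5 vanishes. Assume a reference hazard of 0.12 per year and mean follow-up of 0.6 against 0.9 year: [1 − exp(−0.18 × 0.6)]/[1 − exp(−0.12 × 0.9)] = 1.00. Under constant discontinuation this needs about 68% of the subgroup to stop, against about 19%.

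**Conclusion.** The point holds in a limited form. SAP 7.8.1 contrasts ADRs between subgroups by crude ratios of patient counts, while time at risk ends shortly after the last intake and may differ between subgroups. The planned exposure-adjusted rate is not stated to be compared by subgroup. The section also names two different crude measures, which is a plain inconsistency.

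The size depends on assumed stopping rates. With 10% of the reference group stopping, a true rate ratio of 1.5 appears as about 1.38 to 1.21 when 20% to 40% of the subgroup stop, and as 1.46 with equal stopping. If the reference group stops earlier, the error runs the other way. These figures rest on constant hazards and on stopping unrelated to ADR risk. This is a worthwhile improvement to an exploratory analysis; the primary outcome, overall ADR incidence, is not called into question.

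**What to change.** In SAP 7.8.1, for each subgroup factor and including age and renal function because they are priority survey items:

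1. Report patient-years and the ADR rate per 100 patient-years in each category.
2. Report a Cox hazard ratio for time to first ADR with 95% CI, censoring at the end of the treatment-emergent window. A Poisson rate ratio with log time at risk as offset and follow-up period terms would also serve; the SAP's onset periods could supply the terms.
3. Keep the crude ratio beside it, and use either the odds ratio or the risk ratio throughout.
4. State that the time-adjusted measure decides whether the further organ-class and preferred-term tables are produced.

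The cost is one extra model per factor. Treatment dates and time to first ADR are already needed for planned outputs, so nothing new is collected. The downside is the assumption that stopping is otherwise unrelated to ADR risk within a subgroup, which the data cannot verify. That is why both measures should be shown.

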### **7.8.2      Laboratory data**

Descriptive statistics (see summary statistics at 7. Planned analysis) of eGFR at each calculated visit will be summarized in the table.

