9.3.3 Covariates

The following variables based on physician's report will be considered important baseline characteristics and potential risk factors for the outcomes of interest.

Demographics:

Gender, date of birth, indication, pregnancy status, height, body weight, Body Mass Index (derived), waist circumference, hypersensitivity factor (pick up from medical history and concomitant disease data), diagnosed date of T2DM, alcohol habit, smoking history, degree of renal/hepatic functions at baseline

Medical history / Concomitant disease:

Malignant tumor, cardiovascular/cerebrovascular disease, heart failure (severity for cardiac failure for patients with cardiac failure (NYHA classification)), urinary tract infection, genital infection, hypertension, osteoporosis, dyslipidaemia, intestinal obstruction, gout/hyperuricaemia, others, presence or absence of diabetic concomitant diagnosis (neuropathy/nephropathy/retinopathy)

Previous / Concomitant drugs and therapies:

Antidiabetics (in the 3 months before newly starting TRADIANCE):

Dose, daily frequency, start and end date

Concomitant drugs:

Dose, daily frequency, start and end date, reason for use, route of administration

Exercise and diet therapies:

Start and end date, compliance

Administration of TRADIANCE® Combination Tablets AP or BP:

Dose, daily frequency, start and end date, primary reason of discontinuation, compliance

Compliance:

All previous antidiabetics drugs compliance, TRADIANCE® Combination Tablets AP or BP compliance

Electrocardiogram:

If a resting 12-lead electrocardiogram (ECG) will be performed by investigator's order during the PMS and the investigator should review the ECG data and record the results (abnormal Yes or No) in the Electronic Case Report Form (eCRF).

Blood pressure and pulse rate (if applicable):

Systolic / diastolic blood pressure, pulse rate

Physical examination:

Body weight

Laboratory tests (blood biochemistry and urinalysis) (if applicable):

Haematology: Erythrocyte count (RBC), haemoglobin (Hb), haematocrit (Hct), leukocyte counts (WBC) , platelet count

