ANNEX 2. FLOW CHART OF VARIABLES

Item	Time point Before first administration of TRADIANCE® Combination Tablets AP or BP	Observation period ^{*1}			
		Week 12	Week 26	Week 40	Week 52 or at discontinuation
Registration	X ^{*2}				
Demographics	X				
Physical examination (Body weight, height)	X	X ^{*3}	X ^{*3}	X ^{*3}	X ^{*3}
HbA1c and fasting plasma glucose	X	X	X	X	X
Concomitant disease/ medical history	X				
Waist circumference	X				
Prior Antidiabetic drugs	X ^{*4}				
Administration status of TRADIANCE® Combination Tablets AP or BP		X (Record throughout the observation period)			
Concomitant drug and Concomitant therapy	X*	X (Record throughout the observation period)			
Blood pressure, pulse rate and ECG	(X)	(X)	(X)	(X)	(X)
Pregnancy status ^{*5}	X (confirm throughout the observation period)		X (confirm throughout the observation period)		
Laboratory tests	(X)	(X)	(X)	(X)	(X)
Adverse events		X (Examine throughout the observation period)			

*1: Time points during the observation period are approximate. Collected data should be reported as of the closest available visit.

*2: Patients administered TRADIANCE® Combination Tablets AP or BP will be registered within 14 days from whenever the day of first administration is possible.

*3: Body weight only

*4: From 3 month before first administration of TRADIANCE® Combination Tablets AP or BP

*5: Only for female patients

(X): If applicable

eCRF (electronic case report form): At 26 weeks, 52 weeks, and each time an adverse event has occurred, data in corresponding observation period should be entered into the eCRF and transmitted using the EDC system.

APPROVAL / SIGNATURE PAGE

[figure not shown]
[figure not shown]
[figure not shown]
[figure not shown]
[figure not shown]
[figure not shown]
[figure not shown]
[figure not shown]
Document Number: c20025178

Technical Version Number: 2.0

Document Name: 1275-0026-nis-protocol-revision-01

Title: Post Marketing Surveillance in Japan on Long Term Drug Use of TRADIANCE Combination Tablets AP and BP in Patients with type 2 Diabetes Mellitus

Signatures (obtained electronically)

Meaning of Signature	Signed by	Date Signed
Author-Clinical Trial Leader		23 Nov 2018 08:10 CET
Approval-EU Qualified Person Pharmacovigilance		23 Nov 2018 08:37 CET
Approval-Team Member Medical Affairs		23 Nov 2018 09:26 CET
Approval-Therapeutic Area		23 Nov 2018 09:51 CET
Approval-  Pharmacovigilance		23 Nov 2018 11:10 CET
Approval-Team Member Drug Safety		23 Nov 2018 11:15 CET

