## **6. GENERAL ANALYSIS DEFINITIONS**

### **6.1 TREATMENT(S)**

For basic study information on treatments, please refer to NIS Protocol Section 4. The technical specification for treatment set-up is described in the analysis data set (ADS) plan.

For effectiveness analyses, data up to 7 days after last treatment intake will be considered as on treatment for HbA1c and 1 day for FPG. For safety analyses, data up to 7 days after last treatment intake will be considered as on treatment for AE, 1 day for weight, blood pressure and pulse and 3 days for laboratory measurements.

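### eGFR is summarised visit by visit with no within-patient change, so differences between visits can reflect who was tested rather than how patients changed

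*SAP*

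**What the plan says.** SAP 7.8.2 is a single sentence. It says that descriptive statistics "of eGFR at each calculated visit will be summarized in the table", and refers to SAP 7 for which statistics these are: "the set of summary statistics is: N / Mean / SD / Min / Q1 / Median / Q3 / Max". Section 7.8.2 mentions no change from baseline, paired summary, shift between renal grades or model. The mixed model in the protocol abstract covers HbA1c and FPG only.

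Creatinine, from which eGFR is calculated, belongs to the list that protocol 9.3.3 heads "Laboratory tests (blood biochemistry and urinalysis) (if applicable", closing bracket omitted. Protocol Annex 2 marks laboratory tests as conditional at baseline and at weeks 12, 26, 40 and 52. HbA1c and FPG carry an unconditional mark at the same points.

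The protocol abstract ends observation at 52 weeks or when treatment is stopped. SAP 6.1 allows "3 days for laboratory measurements" after the last intake. SAP 6.6 shows no missing-data rule for laboratory values.

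Two passages make renal function relevant. The priority survey items in protocol 11.2 include "safety of administration to patients with renal impairment or elderly patients (important missing information"), and SAP 7.8.1 lists "Renal disorder" among the important potential risks.

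**The concern.** A table with one eGFR column per visit invites reading across. That reading is sound only if much the same patients stand behind each column, and nothing in the visible plan ensures this.

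Two plausible forces change the mix. If patients with impaired renal function are tested more consistently than others, later visits contain relatively more of them and the mean drifts down. If those patients stop treatment more often, later visits contain fewer of them and the mean drifts up. The documents do not say which force dominates, or whether either operates.

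At stake is any sentence in the report about eGFR over 52 weeks. Adverse event tables do not fully replace it. The mandatory collection list in protocol 11.2 is all ADRs and all fatal AEs, although the same section and 9.4 also ask for prompt entry of any AE. Collection of a non-fatal decline that nobody judged drug-related is therefore not assured. The eGFR table is the one visible summary of renal function that does not depend on someone reporting an event.

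**Working it through.** The documents give no eGFR values, testing rates or discontinuation rates, so there is no plan figure to reproduce. The only design calculation (protocol 9.5) concerns hypoglycaemia and has no bearing here. All inputs below are assumptions chosen to show the mechanism.

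**Formula.** Take two groups with mean eGFR m1 (higher) and m2 (lower), making up fractions w1 and w2 of all patients as measured at a visit. The visit mean is (w1·m1 + w2·m2)/(w1 + w2). If nobody changes, the difference between two visits is minus the shift in the lower group's share of measured patients, times the gap m1 - m2.

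**Common assumption for (a) to (c).** 70% of patients have eGFR 75, 30% have eGFR 45, and no patient changes.

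**(a) Testing becomes more selective.** Tested at baseline: 80% and 95%. At week 52: 50% and 90%.
- Baseline: w = 0.70×0.80 = 0.560 and 0.30×0.95 = 0.285. Mean = (0.560×75 + 0.285×45)/0.845 = 64.88.
- Week 52: w = 0.70×0.50 = 0.350 and 0.30×0.90 = 0.270. Mean = (0.350×75 + 0.270×45)/0.620 = 61.94.
- Apparent change: -2.9.
- Cross-check: the lower group's share goes from 0.285/0.845 = 33.7% to 0.270/0.620 = 43.5%. That is 9.8 points, and 0.098×30 = 2.9.

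**(b) Retention differs.** Tested: 80% in both groups throughout. Still treated at week 52: 90% and 60%.
- Baseline: (0.560×75 + 0.240×45)/0.800 = 66.0.
- Week 52: w = 0.560×0.90 = 0.504 and 0.240×0.60 = 0.144. Mean = (0.504×75 + 0.144×45)/0.648 = 68.3.
- Apparent change: +2.3.

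**(c) Both together.** Testing as in (a), retention as in (b).
- Baseline: 64.88, as in (a).
- Week 52: w = 0.350×0.90 = 0.315 and 0.270×0.60 = 0.162. Mean = (0.315×75 + 0.162×45)/0.477 = 64.81.
- Apparent change: -0.1. The two forces almost cancel.

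**(d) A true fall is hidden.** Different assumptions: 1000 patients, 20% with mean eGFR 50 and 80% with mean 85; every patient falls by 3.
- Baseline, tested 90% and 60%: 180 and 480 patients. Mean = (180×50 + 480×85)/660 = 75.5.
- Week 52, tested and still treated 60% and 60%: 120 and 480 patients. Mean = (120×47 + 480×82)/600 = 75.0.
- Apparent change: -0.5 against a true change of -3.

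**Range.** For shifts of 5 to 15 points in the share and gaps of 20 to 50, the artefact runs from 0.05×20 = 1.0 to 0.15×50 = 7.5 mL/min/1.73m², in either direction.

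**What pairing does.** Change from baseline in patients with both values returns 0 in (a) to (c) and -3 in (d). It does so because the assumed change is the same in both groups. If patients whose eGFR falls are those who stop or go untested, the paired change is biased too.

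**The case against.** The strongest reply is that this table carries little weight. eGFR over time is not an endpoint: the primary outcome is ADR incidence and there is no secondary outcome. No test, threshold or conclusion in the visible plan rests on the by-visit statistics. Protocol 9.9 already names selection bias and loss to follow-up and says that comparisons and causal conclusions cannot be made. That stands, and it keeps the point small. It does not remove it, because a paired change is equally descriptive and answers the question a reader will bring to the table.

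Four stronger readings are tempting, and the documents do not support them.
- *eGFR is reported by its mean alone.* It is not: N, SD, median, quartiles and range are given, and SAP 7 also provides listings of individual values. But N does not show who was tested, medians and quartiles move with case mix as the mean does, and listings are not a summary of change.
- *The renal priority survey item is left without a sound analysis.* That item concerns safety in patients who have renal impairment, not the eGFR trajectory of the cohort. SAP 7.8.1 summarises priority items separately, and renal disorder has its own AE and ADR summary.
- *This is the whole plan for eGFR.* SAP 6.4 and 7.6 and protocol 9.7.2 are not in the visible text, so a further analysis cannot be excluded. Section 7.8.2 itself has no gap and points to none.
- *The by-visit means will be biased by a known amount.* Every magnitude is assumed, and case (c) shows that the net effect can be close to zero.

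**Conclusion.** The point holds as a modest one. The visible eGFR plan is cross-sectional at each visit, testing is optional, and patients who stop leave the data. Differences between visits therefore cannot be read as within-patient change. Illustrative shifts with no true change are about -2.9 and +2.3 mL/min/1.73m²; with other assumed inputs, a true fall of 3 appears as -0.5. These rest entirely on assumed eGFR levels, testing rates and retention rates, so they show that the artefact is possible, not that it will occur. The primary ADR result is unaffected. The consequence is limited to a supplementary safety table and to statements drawn from it.

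**What to change.** In SAP 7.8.2, keep the by-visit statistics and add change in eGFR from baseline at each calculated visit in patients who have both values.
- Show N, the baseline value of those same patients, the visit value and the change. Setting the same-patient baseline beside the baseline of all tested patients makes selection visible.
- State that any comment on eGFR over time rests on this table and not on the by-visit statistics.
- State that selective testing and discontinuation can still bias the paired change.
- If the change is also shown by the baseline renal grades of protocol 9.3.3, keep it descriptive and warn of regression to the mean, since the grade comes from the same baseline value from which change is measured.

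The cost is one extra table from data already collected, with a smaller N at each visit, and a short SAP revision. No new data collection is needed.
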